[Study Withdrawal & No Show Protocol](#)

The protocols in this section involve changing a participant's status using the "Change Status" button on the individual participant's page in the tracking system. Further instructions on this process, can be found in the "[Using the Tracking System](#)" section on page 70.

Withdrawal

A participant could be considered withdrawn under two circumstances:

1. When a participant asks to be withdrawn from the study. When this request occurs, a withdrawal form is completed by the study coordinator or RA. This request is initiated by the participant and occurs at any time.
2. Or, during study contact for non-data collection activities, such as making the reminder call. This action is initiated by a member of the study team.

In either case, the participant should be marked "Withdrawn."

Investigator Withdrawal

Participants are subject to investigator withdrawal when:

1. A pediatric patient is found to have a confirmed genetic related diagnosis during Visit 1. This would be considered “Investigator Withdrawal-At Clinic Visit 1 (Intervention 1)”. These participants will/can complete the Intake Survey, Pre- and Post-Visit Surveys but are not considered for Genetic Sequencing part of the study (i.e. intervention 2). Parents can receive up to \$70 in compensation, and the child will receive a nonmonetary gift.
2. NCGENES study staff unable to attend the research/clinic appointment (e.g. due to illness or other conflict). Participants that attend their clinical appointments, can receive up to \$40 (\$10 for parking and \$30 if they submit a completed Intake Survey).
3. A participant (child or adult) was ineligible at the time of enrollment BUT this was only discovered after participant was already enrolled (e.g at Visit 1). For example, a participant has a confirmed genetic diagnosis prior to the enrollment (i.e. this diagnosis does not occur at Visit 1), but this diagnosis was not disclosed during the enrollment call and was not found in the patient’s medical record. In these cases, all the data associated with this participant will be removed for the analytic database.

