 - o If the participant is found to be ineligible for reasons which preceded their enrollment, the following phrase should be copied into the reason text box when changing the participant’s status: “Participant was ineligible at the time of enrollment BUT this was only discovered after participant was already enrolled, thus participant coded as ‘Investigator Withdrawal’ and data removed from analytic database.”

No Shows

Participants are considered a *No Show* if the study staff are unable to complete the research visit with a consented participant.

No Show – Research Visit ONLY

A participant should be considered a “*No Show – Research Visit ONLY*” if there is not enough time for the study staff to complete the research visit tasks (e.g. pre- and post- survey or consenting process) at the time of the clinic visit AND the participant must be assented and is thus ineligible for phone consent. This can happen if a participant arrives to the clinic at or after their scheduled clinic appointment time or if the participant has multiple clinical visits that conflict with the research visit protocol. In this case, participants are censored from the study.

No Show – Research and Clinic Visit

A participant should be considered a “*No Show – Research and Clinic Visit*” if they miss their clinical appointment completely. In this case, the participant is given 30 days to reschedule their appointment.¹ If they do reschedule their appointment in 30 days to some date in the future, they can still participate in the study. Participants may be rescheduled up to 3 times.

If the participant is not rescheduled for an appointment within 30 days after their original appointment date, the participant is coded with a final status of “*No Show*”. The SC will periodically monitor EPIC to determine if the participant has been rescheduled and work with the tracking system team and other study team members to complete necessary steps based upon the participant’s reschedule status. The study biostatistician will generate regular reports to indicate participants whose statuses should be changed to a “*No Show*.”

Alert Protocol for NCGENES 2 Distressed Adult Participants

Parent/Caregiver participant distress is evaluated through the parent’s or caregiver’s completion of study surveys. When responses are entered into the tracking system, the system will score the GAD7 (anxiety measure) and the PHQ8 (depression measure). The measures appear on the questionnaires listed below:

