 - i. Patients designated as ‘New visit’ to either (Peds Genetics or Peds Neuro) clinic because it has been > 3 years since their last visit to the clinic (essentially, they are a return patient to the same clinic)
 - ii. Patients designated as ‘New visit’ to either (Peds Genetics or Peds Neuro) clinic but have been seen in <=3 years ago in that same clinic. This can be determined by a review of the medical record where it can be clearly seen that this patient has been seen by the same or a different doctor in that same clinic in the past. For example, a patient has been seen 2 times in a clinic and then calls needing an immediate appointment and the MD tells the scheduler to put them in ANY type of clinic appointment available and the scheduler places the return patient in a “New visit” slot.

Phenotypic Eligibility Criteria

1. Inclusion Criteria

[figure not shown]
[figure not shown]
[figure not shown]
[figure not shown]
- a. One of the following conditions/initial referral reasons:

- i. Epilepsy and seizures (Any seizures if with developmental delays. Any seizures onset prior to 6 months old. But not for example febrile seizures or a single afebrile seizure in a child with typical development).
- ii. Neuromuscular disorder (this may include muscle weakness, elevated CKs, neuropathies, arthrogryposis, etc)
- iii. Brain malformation (this includes lissencephaly, schizencephaly, megaencephaly, polymicrogyria, pachygyria, etc)
- iv. Intellectual disability/autism spectrum disorder with intellectual disability/developmental delay
- v. Hypotonia (unexplained)
- vi. Inborn errors of metabolism suspected
- vii. Movement disorder (dystonia, ataxia, etc)
- viii. Other conditions that are considered have a genetic etiology (such as severe congenital central hypoventilation syndrome).
- ix. Microcephaly/Macrocephaly with developmental delays or any that are >2.5 SD from normal.
- x. Metabolic indications that WILL be included [represents 30% of metabolic patients] are:
 - 1. R/O mitochondrial disorder
 - 2. R/O metabolic with neurologic component like;
 - a. Hypotonia
 - b. Ketosis
 - c. Hypoglycemia
 - d. Hepatomegaly
 - e. Cyclic vomiting
 - f. Splenomegaly
- xi. Chromosome Abnormality (some select cases see below)
 - 1. Note: A microarray VUS would still effectively be in a “diagnostic odyssey” and be eligible, however it could also be a real “positive” in which case the referral would be for post-test counseling and the case would be ineligible.

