- xii. Hearing loss
- xiii. Dysmorphic features
- xiv. Skeletal Dysplasia (e.g., achondroplasia, OI, Unknown)
- xv. Multiple congenital anomalies
 - 1. Includes multiple congenital anomaly syndromes with no etiology (e.g., VATER, CHARGE (make sure not related to CHD 7 gene mutation), Pierre Robin
- xvi. Rhabdomyolysis
- xvii. Hereditary/Childhood Cancer while typically out of scope for NCGENES 2, should not be an absolute exclusion criterion. There are some multisystemic genetic syndromes where cancer can be seen (e.g., Wilms tumor in the setting of overgrowth, neonatal hypoglycemia, and exomphalos would suggest Beckwith-Wiedemann syndrome). When such a condition is described provide as much detail as possible related to any other clinical findings, path report and send to [name] for determination of eligibility.
- xviii. Fetal Alcohol Syndrome – while an entirely non-genetic disorder BUT may be confused with other genetic syndromes. Many cases of FAS are challenging for referring pediatricians to diagnose and thus in some cases these referrals will be considered eligible. Specifically, if *developmental delay* is included as a finding in the child with FAS referral we will consider them ineligible. We will let the geneticist rule the child in or out during the clinic visit. If the clinical geneticist diagnosis FAS then this will be a ‘diagnosis at visit 1’ and thus these patients will be investigator withdrawals with the typical ineligibility status sentence.

2. Exclusion criteria

- a. Any known history of the following acquired conditions such as ischemic encephalopathy (including perinatal stroke), CNS infection (such as meningitis or encephalitis), brain trauma, autoimmune/inflammatory disorder or other acquired injury to brain/nerve/muscle. Macrocephaly in a patient with known hydrocephalus/shunt.
- b. Patients who have a known genetic diagnosis that explains the clinical presentation.
- c. Most metabolic will NOT be included (e.g., abnormal newborn screen) [represents 70% of metabolic patients]
- d. Café au lait (isolated)
- e. Trisomy 21, 18, 17, 16p
- f. Microdeletion 22q
- g. Family history of a known genetic condition (e.g., CF, being referred for genetic counseling)
- h. Short stature (isolated)
- i. Obesity (isolated)
- j. Failure to thrive (isolated)
- k. Cleft lip and/or cleft palate (isolated - not part of a syndrome)
- l. R/O connective tissue disorder/hypermobility
 - i. R/O Ehlers-Danlos Syndrome
 - ii. R/O Marfan Syndrome

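### The fetal alcohol syndrome criterion contradicts itself on eligibility, and appears to send a diagnosis made at Visit 1 down the withdrawal route that removes already randomized families from the analysis

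*Protocol*

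**What the plan says.** **Eligibility (Appendix I, Phenotypic Eligibility Criteria, inclusion criterion xviii).** FAS is described as non-genetic but easily confused with genetic syndromes, and "thus in some cases these referrals will be considered eligible". A sentence beginning with the word Specifically follows: if developmental delay "is included as a finding in the child with FAS referral we will consider them ineligible". The next sentence reads "We will let the geneticist rule the child in or out during the clinic visit". Criterion iv of the same list makes "Intellectual disability/autism spectrum disorder with intellectual disability/developmental delay" a qualifying referral reason in its own right.

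**Coding (same criterion).** If the geneticist diagnoses FAS, this counts as a diagnosis made at Visit 1, and "these patients will be investigator withdrawals with the typical ineligibility status sentence".

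**Withdrawal rules (Study Withdrawal & No Show Protocol, Investigator Withdrawal).** Two of the listed circumstances matter here:

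- Item 1: "A pediatric patient is found to have a confirmed genetic related diagnosis during Visit 1". "These participants will/can complete the Intake Survey, Pre- and Post-Visit Surveys but are not considered for Genetic Sequencing part of the study". No removal of data is mentioned.
- Item 3: the participant was already ineligible at enrollment and this was found only later. All of that participant's data are removed. The example given expressly sets aside a diagnosis made at Visit 1. Staff must paste a standard sentence that ends "and data removed from analytic database".

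**The concern.** Two things look wrong.

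First, a screener cannot apply criterion xviii consistently. It admits, excludes and defers in three consecutive sentences, and different sites could resolve that in opposite ways.

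Second, the criterion labels the event as belonging to one withdrawal route and documents it with the sentence of another. Randomization 1 takes place on the enrollment call, before Visit 1. A family removed from the analytic database for what the geneticist concludes at Visit 1 is therefore a post-randomization exclusion, made after the pre-visit materials have been sent. Exclusion for a fact established before randomization is easier to defend than exclusion on a judgement reached after the intervention has been delivered.

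**Working it through.** No sample size, power or event figure lies behind this point, so the check is a comparison of texts.

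**Step 1: does the eligibility wording hold together?**

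1. Criterion xviii stands in the inclusion list and opens by admitting some FAS referrals.
2. The word Specifically should introduce the cases admitted. The sentence it opens excludes children instead.
3. The next sentence gives the decision to the geneticist at the visit. Under Participant Selection, Participant Ineligible is a final status with no further action, so a child screened as ineligible does not come to Visit 1 as a participant.
4. One reading avoids the contradiction: only FAS referrals without developmental delay go on to the geneticist. It is grammatically possible. It fits poorly with Specifically, with the place in the inclusion list, and with criterion iv, where developmental delay itself qualifies.

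Result: as written, the rule contradicts itself or needs a strained reading.

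**Step 2: which withdrawal route applies to FAS found at Visit 1?**

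| Feature | Item 1 | Item 3 | Criterion xviii |
|---|---|---|---|
| When the reason is established | Visit 1 | After enrollment, for a reason that preceded it | Visit 1 |
| Kind of diagnosis | Genetic | Any ground of ineligibility; the example is a genetic diagnosis | Non-genetic |
| Sentence to paste | None given | The ineligibility sentence | An ineligibility sentence, not reprinted |
| Data | Surveys can be completed; removal not mentioned | All removed | Follows the sentence |

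Criterion xviii takes its timing label from item 1 and its sentence, apparently, from item 3. Item 3's example sets aside a Visit 1 diagnosis. For a child whom criterion xviii had admitted, a statement that the child was already ineligible at enrollment would also be untrue on the criterion's own terms.

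**Step 3: have these families been randomized?**

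Yes. Under Randomization 1, assignment to Intervention 1 happens when the parent consents on the enrollment call.

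**Step 4: how does this sit with the stated analysis?**

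Appendix III, item 5c, says an intention-to-treat analysis will be done. Removing randomized families for a Visit 1 finding is in tension with that.

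**Step 5: how many?**

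The document gives no FAS referral or diagnosis rate. As an assumption only, for scale against the planned enrollment of 850:

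- 0.5%: 0.005 × 850 = 4.25 families
- 1%: 0.01 × 850 = 8.5 families
- 2%: 0.02 × 850 = 17 families

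None of these is an estimate.

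**The case against.** Several points on the other side stand.

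- **Item 1 does not literally cover FAS.** It is limited to a genetic diagnosis, and the criterion calls FAS non-genetic. Nor does item 1 say outright that data are kept. A reader might infer that the withdrawal rules promise retention and criterion xviii breaks that promise. The text does not go that far: it leaves a gap.
- **The sentence is identified by inference.** Criterion xviii does not reprint it. The inference is strong, because only one standard ineligibility sentence for enrolled participants appears in the document.
- **Item 3 has an arguable basis.** A child with FAS never had the genetic etiology that eligibility requires, so the reason could be said to precede enrollment. But the same is true of any condition diagnosed at Visit 1, and the protocol separates the routes by when the diagnosis is made. The criterion itself applies the Visit 1 label.
- **The intention-to-treat remark is brief.** It occurs in a note on drop-out and the balance between arms, and it defines no analysis population. That supports speaking of tension, not of a breach.
- **The two problems fall largely on different children.** If screeners apply the exclusion, children with developmental delay are never randomized and have no data to lose.
- **Doubtful cases are referred upwards.** Participant Eligibility and Participant Eligibility Tracking send unclear cases to the study physician, project director or PI, and Appendix I expects to be revised.

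A reader might also infer bias between arms, since parents given the question list are told to hand it to the physician. Nothing in the document suggests that this would alter whether a geneticist diagnoses FAS, so that inference is not supported.

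**Conclusion.** The point holds as a minor one. The eligibility wording of criterion xviii contradicts itself and must be reconciled; this review takes no position on which rule is right. The coding instruction joins a Visit 1 diagnosis to a sentence that appears to remove the data of families already randomized to Intervention 1, although the withdrawal rules keep that sentence for ineligibility preceding enrollment.

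The second part rests on two assumptions: that the sentence meant is the one printed under Investigator Withdrawal, and that some FAS referrals are enrolled and then diagnosed at Visit 1. The number is unknown and probably small, so a material effect on the Intervention 1 comparison is not shown. What is shown is an instruction that, followed as written, would take randomized families out of the analysis on a post-randomization judgement.

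**What to change.** 1. In criterion xviii, reconcile the sentences on eligibility, on developmental delay and on the geneticist's decision so that they state one rule. The choice of rule belongs to the investigators.
2. In the same criterion, drop the reference to the ineligibility sentence for FAS diagnosed at Visit 1.
3. Under Investigator Withdrawal, widen item 1 to any diagnosis first made at Visit 1 that ends participation before Intervention 2, including a non-genetic one such as FAS. Say expressly that Intervention 1 data stay in the analytic database.
4. Keep item 3 and its sentence for ineligibility that preceded enrollment.

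The cost is a few sentences in Appendix I and in the withdrawal section, with no change to sample size or procedures. If any participant has already been coded this way, the record should be checked and the Intervention 1 data restored.

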Appendix II. Study Statuses

Appendix III. Randomized Recruitment

Recruitment sampling and randomization in NCGENES

2/14/2018

1. **Recruitment Sampling** (randomization recruitment) – Using the last full year (2016) of patients coming to relevant UNC clinics where NCGENES2 patients are seen identify the frequency of the following groups (% of total patients). Operationally recruit all African Americans/Hispanic/Medicaid (under-served/under-represented) patients and calculate sampling proportions for the remaining group (served). Randomly assign a sample weight to patients in this group and recruit only if the randomly assigned proportion is at or below the sampling weight.

Randomized Recruitment Charts for UNC NCGENES 2 Clinics									
Pediatric Genetics and Metabolism Clinic		Project number in UNC clinics	% selected randomly for study	Number selected	Minus 10% ineligible	Eligible	Minus 30% non-responders or refusals	Projected cases enrolled	Proportion
Per yr*									
AA - Hispanic-Medicaid	1438	100%	1438	144	1294	388	906	60%	
Non-AA - Non-Hispanic - Non-Medicaid	1500	64%	960	96	864	259	605	40%	
ALL							1511	100%	
Pediatric Neurology Clinic									
AA - Hispanic-Medicaid	3035	100%	3035	304	2731	819	1912	60%	
Non-AA - Non-Hispanic - Non-Medicaid	2640	77%	2033	203	1830	549	1281	40%	
ALL							3193	100%	
Both Clinics Combined									
AA - Hispanic-Medicaid	4473	100%	4473	447	4025	1208	2818	60%	
Non-AA - Non-Hispanic - Non-Medicaid	4140	71%	2993	299	2694	808	1885	40%	
ALL							4703	100%	
**Assumes proportions (served/under-served) of ALL clinic cases (shown here) is equal to the proportion of cases who fit clinical criteria									
*** Likely non-response rates will differ by group and will need to be adjusted over time to allow better % selected estimates									

2. Study intervention randomization #1 (Pre vs. No Pre-visit prep) – Create randomly permuted blocks of size 2-8 for each of the 4 sample groups above until the targeted number of enrolled is achieved.
3. Study intervention randomization #2 (Genomic Sequencing (GS) vs. No GS) – Should make sure that those in pre vs No pre-visit prep are equally distributed into +/- GS groups
 - a. I agree – per [name]
4. Both interventions are randomized 1:1
5. Concern and Question:
 - a. While we will apply randomized recruitment (sampling/selection) to balance proportion of underserved to served at enrollment this will not ensure balance of served and underserved within intervention arms, true? Is there any way to ensure balance of served underserved within intervention arms?
 - i. I thought it would be balanced. If I understand it correctly, we are going to randomize intervention/control assignments 1:1 ratio in each of the 4 groups above. Therefore, the underserved and served ratio is still 3:2 in the intervention group, as well as in the control group. Per [name]
 - b. Should subjects be randomized to both arms at the same time. Concern that some participants in arm 1 with pre-visit prep of certain demographic group will be burdened and drop out before GS randomization.

- i. I feel drop-out is probably the main reason for unbalance. If we do have the same drop-out rate between underserved and served, then 3:2 ratio remains, as shown in your table. If we have the same drop-out rates between intervention and control, then 1:1 ratio between intervention and control remains, as well as the 3:2 ratio between underserved and served.- per [name]
- c. Should we do something at block randomization to account for these concerns. [name] would not recommend any other adjustments at randomization to address this. Indeed. The block randomization can guarantee the balance between intervention and control, but without balanced drop-out, the final sample cannot reach the ideal ratio. However, we will do intention-to-treat analysis, so the intervention and control ratio should still be balanced.-per [name]
- d. Per [name], he will generate trial randomization list but wants to be sure that the numbers on the list are assigned sequentially and matched to a specific ID#. The patient tracking system will handle this. He will send randomization list when we let him know that we are ready to go. The randomization scheme will be applied to individuals in the study as they enrolled. There will be a different randomization list for each site.

REFERENCES: [Weinberg CR¹](#), [Sandler DP](#). Randomized recruitment in case-control studies. *Am J Epidemiol*. 1991 Aug 15;134(4):421-32.

Appendix IV. Pre-Clinic and In-Clinic Activities list for Research Assistant and Study Coordinator

RA Pre-Clinic and In-Clinic Activities (updated 10/7/2019)

Before clinic visit

1. Check NCGENES calendar for clinic location and study ID of scheduled participants
2. Obtain clinic consult room
3. Charge all electronic devices (audio recorder, iPad, tablet)
4. Be sure that all movies and cartoons on Netflix have been refreshed each week
5. Pack the following:
 - All chargers for electronic devices
 - All electronic devices (tablet should have stylus)
 - Create participant study folders (see chart order document)¹
 - Pen
 - Laminated instructions for physicians
 - Laminated sheet with MDs and genetic counselor names

To do in clinic

1. Sit outside Pediatrics clinic to look for relevant patient check in²
2. Correspond with the study coordinator by text regarding arrival of patient noted in the EMR
3. Login to UNC-guest/relevant hospital internet access (set up so automatic)
4. Open VPN and connect, which ensures secure access
5. Once connected, open Chrome and click on NCGENES tab
6. Click on 'participants' and in the URL line enter participant ID number or order participant list by ID and click on participant's name to open task list
7. Approach patient in clinic waiting area, confirm parent's/patient's name and introduce yourself and your relationship to the NCGENES
8. Confirm appointment in tracking system
9. Collect intake from parent, place in participant's folder and indicate receipt of form in tracking.
 - a. If patient doesn't have form, provide paper intake with postage paid return envelope and complete necessary items in the tracking system for that scenario
 - b. If there is 45 minutes prior to the clinic appointment AFTER completion of all pre-clinic visit research and clinical activities (e.g. height and weight), the parent can complete the intake form on paper in the clinic room
 - c. A note must be made in the participant's chart in the tracking system if any part of the Intake form is completed AFTER the clinic visit
10. Open a second web page and navigate to <https://ncgenes2.sirs.unc.edu/surveys>³
11. Go back to specific patient's 'task' page and copy the survey code for pre-visit survey and go to second page and paste in survey code
12. Go back to patient task page and close it - leaving only the survey page open. This ensures that the parent cannot see other study participant's details/files
13. Open survey on tablet and hand to parent for completion (with or without stylus or touch). Let parent know to hand you the tablet when done. Stay nearby for questions/tablet challenges.
14. Obtain tablet from parent (click finish, if needed)
15. Re-open a patient specific 'task' page and confirm pre-visit 1 parent survey now has a 'completed' status
16. Click on parent permission to audiotape task and read/state that study is trying to learn about parent and physician communication and would like to audiotape the clinic visit and that if the parent consents they will check "yes" and sign
17. Hand the tablet to the parent to indicate "yes" or "no" and sign

¹ SC or unblinded member of the study team will provide RA with the appropriate post-visit survey for each participant.

² If the patient is approached prior to check in, just do a brief introduction and inform them you will speak with them after check-in - do not want to delay check-in process)

³ Tasks 10-18 may be completed after patient has been weighed, etc. by nurse and placed in exam room.

18. When they return tablet to you, type in the parent's name, then sign and date and type your name as witness before clicking "Finish and finalize"
19. Prior to genetic counselor (or physician) entering the room, turn on audio recorder (side bar), then press record and say the recorder number and participant's study ID number¹
20. Set recorder and case on shelf in clinic room out of reach of patient
21. When done, let the genetic counselor or physician (they sit in work room) know that you are finished, and the patient is ready for clinical visit to begin²

(Both the counselor and physician will need to see patient next)
22. Go to waiting area/consultation room and, if possible, enter the paper intake form into the tracking system,³ while monitoring whether the clinician has concluded their visit
23. At the end of the visit, turn off and collect tape recorder and provide post-visit survey (ideally in the exam room, though the post-visit survey can be administered in the waiting/consultation room if needed)
24. Provide the post-visit parent survey as you did pre-visit survey via a new surveys tab, BUT use the appropriate survey code for the post-visit survey on the participant page
25. While parent is doing post-visit survey, consult with the physician regarding developmental age of child (only if 7 years of age or older chronologically) and any planned blood orders. Also identify if any time sensitive blood collections are needed (e.g., those needed by 3pm, etc.). Relay this information to the Study Coordinator in-person or by text.
26. When parent is done with the survey let them know that you will now take them to the Study Coordinator (who they may have spoken with by phone before today's visit) who will talk to them about a potential next test and provide snacks/reimbursement. When the SC is finished seeing the parent they will direct them to the check-out area and then take them to the phlebotomy area if their child needs to have any blood drawn.
27. Collect the iPad and walk patient and parent to consultation room and hand off folder and patient to Study Coordinator⁴
28. Double check to be sure that you have all tablets, iPads and audio recorders that were brought to the clinic
29. Return to the office and place all electronic devices on chargers in preparation for the next clinic

¹ If unable to record the study ID number, then on the intake form, you received from the parent, write the number of the recorder that was placed in the room.

² NEVER unblind the physician or genetic counselor to the randomization status of the patient (either pre-visit prep or genomic sequencing). If this happens a NOTE should be placed in the participant's tracking system record. The physician and genetic counselor can ONLY be unblinded to patient's randomization status AFTER the physician has completed the post-visit 1 physician survey

³ If the Intake form was not entered by the RA during the clinic visit, it should be entered after the Study Coordinator returns with the folder from the clinic or immediately the next morning. Intake forms should be entered within 24 hours of collection.

⁴ To date we have used the UNC consultation room in Pediatrics clinic (behind check out) primarily, but have also used the cardiology conference room

Study Coordinator Pre-Clinic and In-Clinic Activities
(10/7/2019)

Before clinic visit:

- Log into the NCGENES tracking system¹ to review potential study participants
- Once in tracking, select a referred patient scheduled to visit the clinic three or more weeks from the date of review, starting with the closest appointment date
- Log into EPIC and navigate to the selected patient's medical record information.
- Review this information to confirm the patient's DOB, MRN#, appointment information, and language spoken is the same as that listed in the tracking system.
- If any of the data is different, revise the tracking system to contain the same information that is listed in EPIC and as necessary add a note in tracking to document any changes.
- Review the patient's medical record information in EPIC to determine if the patient meets study's clinical inclusion criteria.
- Make appropriate selections in the tracking system to indicate the patient's study eligibility, per the above EPIC review.
- For ineligible patients, no further action is needed
- For eligible patients:
 - Ask an RA to send the study introduction letter (SC will serve as their back-up)
 - Make enrollment calls
 - Update tracking system to reflect the outcome of enrollment calls
- For participants that agree to be in the study:
 - Based upon randomization for intervention 1, have an unblinded RA create and mail enrollment packet (SC will serve as their back-up)
 - Add participant to NCGENES calendar
 - For participants attending the genetics & metabolism clinic, make a note in MEDGIS that patient is an NCGENES participant
 - For patients attending the neurology clinic, email [name] to inform her of their participation²
 - Inform RA, student volunteer, and [name] of upcoming clinic dates and times
 - Make reminder calls and update tracking system to reflect call outcomes
- 1 to 2 days before clinic:
 - Provide RA attending clinic with the appropriate post-clinic visit survey for each participant
 - Check SC clinic bag to ensure it contains all needed supplies and age appropriate participant gifts (generally there are 2 gift choices per participant)

¹ All actions before and during clinic are in the production version of the NCGENES tracking system.

² The email should contain the patient name, MRN#, appointment date & time, and provider name (generally, SC sends [name] an email twice a month regarding study participants)

To do in clinic:

During initial meeting:

- Introduce yourself
 - Typically, parents are told on the phone that they will meet with [name] or another member of the team in clinic. If you spoke with the family on the phone, introduce yourself accordingly
 - If not, tell the parent you work with [name]
- Tell them what will happen during this time (i.e. discuss the second part of the study, take them to check-out /blood draw). Also tell them at check-out they can get a note for school or work if needed. While the parent is at check-out the SC should stand either outside the consult room door or by the tiles with handmade pictures, etc., to meet the parent and take them to phlebotomy/direct them how to exit the hospital.
- Remind they will receive a copy of the forms discussed (also remind them of this point during/at the end of each consent discussion, depending upon how overwhelmed they seem)
- If assent is needed:
 - Tell parent you will need to talk to their child about the study, since they are at least 7 years old. Also, because of this, both parent and child must agree to participate. Generally, try to say this without the child hearing as they may get excited/make a comment that they don't want to participate (and at this point they have not heard anything about the study). Also, this facet of the study tends to make parents tense up. If so, explain to the parent that this is part of standard practice, is required, and is a way to ensure that kids understand what is taking place.
 - Explain to the parent that you'll discuss the study with them first and then their child, and that they will get a copy of everything that is discussed with them and their child.

Consent form 1:

1. At the top of the form and on all the forms we discuss today is the name of the study investigators and contact information. Pointing out that the phone number is the same one that they have received before in the packet. And that this number and email is what they can use to reach members of the study team.
2. They can decline at any time and that it will not impact their care. Whatever was decided/is done during the study will not change what the Dr. (say provider name) wants to have done.
3. If they decide to continue in the study, regardless of if they are assigned to GS or no GS that we will study their child until they are 18 by looking at their medical records and insurance information. Once they turn 18 the link between their name and study ID number will be removed.
4. We are looking at medical records and insurance information for items around why they came to clinic today. That when we use this information to report on study findings, we report in generalities, like for example we saw 850 families and from 50 we learned X and from 150 we learned Y. Also mention that we place information in public databases, which is something that researchers do to learn from each other, but this information is included without any personal information on study participants.
5. Participation will not involve an additional trip to UNC, we understand that no one lives close, so the study was designed in such away as to not have them make a trip to UNC only for the study. Which is why we try to have study activities done when they are already coming.
6. What will happen today is, if they are assigned to have testing and they decide to do so, that for their child participation means giving a little extra blood today. For them it means doing a phone interview about 6-8 months from today and then another phone interview about 6-months after that. If they are assigned to no GS or decide not to have testing, then there are no activities for their child, but that they will still have the phone interviews.
7. The study's funder is part of the NIH (the part of government that funds most research).
8. The IRB is the Institutional Review Board, which is the organization that approved us to do this study and that they make sure researchers do what they say they will do. If they do not think this has occurred, they can contact the IRB with or without giving their name to discuss the issue.
9. The IRB's number is included in the consent, and that they will get a paper copy of the consent after signing.
10. The IRB requires that we have information in the consent about future use of the data, so this section discusses this use and that they can still be in the study regardless of if they decide to have or not have their information stored in the separate database.
11. Discuss the future use section of the consent and offer to let the parent read it on the screen.

12. At the end of reviewing consent form, inform the parent that in by signing this form they are agreeing to allow us to
 - 1) flip the coin to see if they are or are not offered GS testing
 - 2) to look at their child's medical and insurance information regarding information around why they came to clinic today, until their child is 18
 - 3) that we will have to obtain HIPPA consent, since this consent is what allows us to look at their child's medical and insurance records.
13. Ask if they will sign consent form 1.

HIPPA Consent:

1. Acknowledge they are likely familiar with HIPPA due to previous trips to the doctor/hospital.
2. Their signature is needed because it allows us to receive and share information with other HIPPA covered entities.
3. Point out below differences with giving us HIPPA consent versus other times they typically encounter HIPPA:
 - Although they can withdraw from the study at any time by calling, that to withdraw HIPPA authorization requires notification in writing by email or letter, because it involves medical records, etc. The phone number and email address are at the top of the consent forms.
 - Because of the role of NIH and the IRB they can audit the project and that during this audit they may look at their child's research records. This look may reveal some of their child's medical/insurance information or they may ask to see this information to clarify a question. They are not HIPPA covered entities, but we expect them to treat the information in the same manner as HIPPA entities. Records chosen for an audit are random, and that their child's record may or may not be selected.
 - If they give HIPPA authorization to others, after this project, and there is project information in their child's medical record, that these others will have the project information (unless they restrict access)
4. Offer to let parent read HIPPA consent on the screen

Informed consent 2:

1. GS testing is not a new test, but we are trying to determine if having the test sooner rather than later in the process of learning a reason for why their child came to clinic today, impacts care they receive down the road. For example, if they have more or less additional test than children who do not have GS testing.
2. Test results typically come back into one of three categories:
 - Positive, meaning the change we see is the cause for why their child came to clinic today.
 - Uncertain, means that there is not enough data yet to know if the change we see causes health issues or is part of the many changes that people just have.
 - Negative, means at this time we did not find a change that is related to why their child came to clinic today.
